- 2) Compare rates of infection, complication and progression of the wound to deep partial/full thickness between treatment groups.
- 3) Compare healed wound characteristics, Patient Reported Outcomes and Health-related Quality of Life Outcomes between treatment groups.

2.0 Background and significance:

2.1 Background:

Burn wounds are associated with significant morbidity and mortality as well as Quality of Life impairments for the patient. Burn wounds can be particularly problematic as they can compromise skin integrity potentially allowing microbial invasion and subsequent infection. In fact, thermal destruction of the skin provides an ideal environment for microbial colonization. If left untreated, the infection can spread to a systemic level, further jeopardizing the patient.

Topical management via dressings provide a barrier against microbial infection. The current gold standard for burn wound dressings is silver (nanoparticulate or ionic) and it has shown some efficacy in treating infections but it does not demonstrate an ability to prevent infections and some treatment guidelines even recommend against its use.²⁻³ Although silver dressing is preferred for military use, a retrospective review spanning 10 years of use

in military environments showed that silver was not more effective than other antimicrobial topical treatments⁴ and a meta-analysis with over 2500 surgical patients found silver sulfasalazine was associated with increased infection rates and hospital length-of-stays were two days longer on average.⁵

Other current effective dressings for burn wounds include hypochlorite, hydrogen peroxide, sulfa agents, chlorhexidine, iodine or other dilute antiseptics meant to provide some measure of antimicrobial protection. However, all of these have some proven limitations in facilitating wound healing and also have notable local and systemic adverse effects (see ref 6 for review). Finally, none of the current clinical treatments, have demonstrated evidence of enhanced healing and/or reduced scar formation.

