- 4. Patient education on wound care and daily dressing change per routine care. Dressing to be changed daily by patient or provider. Education also provided as to the treatment agent to be applied daily with the dressing change (SynePure Wound Cleanser and Catasyn Advanced Technology Hydrogel or Silvadene).
- 5. Participants will be asked to complete Subject report questionnaires related to the burn wound, symptoms experienced and effects of injury on their activities of daily living.
- 6. The research coordinator will call the participant twice at timepoint Day 1 and Day 3 to assess participant safety, complications/adverse events and address any questions or concerns that the participant may have encountered.
- 7. Follow-up Visits (Visits 2-8) will occur in the UPMC Mercy Burn Center and will consist of wound evaluation, brief history and physical assessment, vital signs, recording of status change since last visit/interaction, medication review, and adverse event collection. 2D photographs will be obtained of burn wound area at time of physical assessment and Subject report questionnaires and wound dressing assessment /treatment agent application (if wound has not yet healed). Reference to the Schedule of Events included with Protocol for additional detail of study procedures.

Recruitment:

Subjects presenting to the study site for treatment of superficial partial thickness burns will be considered for enrollment. Physicians and licensed clinicians within the burn center area, familiar with the study's inclusion/exclusion criteria will assess for potential patients as they arrive to the

Burn Center Clinic for treatment, a part of their burn practice. If the patient is an appropriate candidate and willing to be considered for the study, he/she will be referred to the research team.

After informed consent has been obtained, the study investigators will conduct screening procedures to determine study eligibility. Should the participant meet criteria, he/she will proceed to randomization on Day 0 prior to treatment application. Enrolled subjects will be randomly assigned per a predefined 1:1 randomization scheme to either the interventional group or control group.

Active Treatment:

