- Completion of Subject Self-report questionnaires that pertain to the burn wound, pain, and other symptoms that experience. Potential effects and relationship to the participant's quality of life and activities of daily living
- Adverse events collection

After this initial visit, the research team will reach out to the participant by phone on Day 1 and Day 3 of the study schema to determine if there are any questions, issues or concerns that the participant may be experiencing. Additionally, they will remind and confirm the next in person visit to the clinic.

Follow-up Visits (Visits 2-8):

These Visits will occur in the UPMC Mercy Burn Center and have a duration of 1-2 hours to complete. These visits will consist of wound evaluation to assess for healing, brief history and physical assessment, vital signs, recording of status change since last visit/interaction, medication review, and adverse event collection. 2D photographs will be obtained of burn wound area at time of physical assessment and prior to wound dressing /treatment agent application (if wound has not yet healed) and subject report questionnaires consisting of SF-12, Wound Experience and Satisfaction questionnaires, Vancouver Scar Scale, POSAS Questionnaires (described in the following section). During the study visit, continued instructions for at home dressing and treatment application will be reinforced.

Subject Reported Questionnaires:

Vancouver Scar Scale Score: The VSS⁹ is a scale to assess the extent of scarring for a given wound by scoring the pigmentation, vascularity, pliability and height of the scar. Each domain is individually scored then the domains are summed to give a total score that range from zero (0) to 13 with zero (0) representing a 'normal' presentation. Validity and reliability of the scale have been documented 10-12 and is commonly used in wound healing research.

SF-12: The SF-12¹³, an abbreviated version of the SF-36, is a patient self-reported twelve questions survey of general health, physical functioning, role functioning (physical and emotional), bodily pain, vitality, mental health, and social functioning. The scale is comprised of two scores: physical component summary (PCS) and mental component summary (MCS). Scores are summarized and normalized. While the survey demonstrates moderate validity and reliability, ¹⁴ the survey is ideal for use as it is brief and commonly used, so comparisons between studies are possible.

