POSAS: The patient and observer scar assessment scale¹⁵⁻¹⁶ is used to measure scar quality. It is composed of a patient reported section and an observer reported section. Each section consists of six items that are scored numerically on a ten-step scale. These are then summed together to make up the total score. There is also an overall opinion section for both the patient and the observer. While validity and reliability are marginal for the POSAS, scores have shown little variance from the gold standard, the Vancouver Scar Scale, and it has the distinct advantage of incorporating the patient's perspective.

Wound Experience Questionnaire: The wound experience questionnaire ¹⁷ consists of three sections regarding the patient's wound. The questionnaire is used for wounds early into the healing process and wounds that have dressings. This has been primary used in patients with surgical wounds but can be adapted to wounds not specifically operative, such as burns. Validity and reliability evidence have not been published but the questionnaire has the unique capability to assess a primary focus of this study. In addition to assessing patient satisfaction with the healing process, the questionnaire also assesses patient satisfaction with the wound dressings as distinct categories.

3.1 Data Collection and Statistical Consideration:

Sample Size Estimation:

In this study, the minimal median difference of three (3) days to healing is determined to be the clinically relevant difference. Given an assumed median time of 15 days to healing for the Silvadene comparator group 18 , a corresponding hazard ratio of 0.8 for the intervention group is anticipated. a sample of 45 in each group (90 total) is required to detect a statistically significant difference [confidence level ($\alpha \leq 0.05) - 95\%$; Power - 80%]. Assuming a 10% attrition, it is recommended to enroll up to 100 subjects to achieve a sample of 90 subjects. This will be easily accomplished in our outpatient burn clinic, with a 400-patient annual volume, and we will use a 3-week evaluation period so that the trial can be accomplished in a year.

Analytic Plan:

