Descriptive statistics will be presented as means and standard deviations for continuous data and as counts and percentages for dichotomous and categorical data. Time-to-event curves with Kaplan-Meier (KM) estimates will be used to compare overall median time to wound healing between treatment groups. Comparison of KM curves will be performed using the log rank test as the curve is assumed to be non-parametric or semi-parametric, and the baseline hazard is not related to the group assignment. Relevant clinical and demographic variables may be assessed for their independent contribution in time-to-event outcome using univariate screening and the hazard is assumed to be relatively constant across the study window. Multiple regression modeling (Cox Proportional Modeling) and adjusted KM curves will be assessed as appropriate. Variables will be included in the multivariate analysis if the univariate screening p-value is < 0.10 and multivariate parameters will be presented as hazard ratios with their corresponding 95% confidence intervals.

Infection, complication, and progression rates will be compared using the Chi-squared test or the Fisher exact test if the data is very unequally distributed within the contingency table, which is anticipated for infection rates. Repeated Measure Analysis of Variance (ANOVAs) will be performed to assess differences in PROs with the days since wounding as the Within-Subjects factor and treatment groups as the Between-Subjects factors. Bonferroni post-hoc analyses may be performed for all statistically significant main effects. Baseline demographic and clinical characteristics will be compared between treatment groups with Independent samples t-test for continuous data and Chi-squared test for dichotomous and categorical data.

Analysis will be performed using SPSS (IBM SPSS Statistics for Windows, Version 25.0. Armonk, NY: IBM Corp.) and statistical significance will be determined at $p \le 0.05$ with the exception of univariate screening as previously described.

Outcome definitions:

- 1. Healed wound: 90% reepithelialization (skin and mucous membrane replacement) of the wounded area.
- 2. Infection: characterized by local new inflammation, heat, purulence as well as new or increased pain, redness and swelling
- 3. Complications other than infection: gangrene, necrosis, periwound dermatisis and/or edema, hematoma, or any other complication determined to be related to the wound and/or treatment

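### Repeated-measures ANOVA for the patient-reported outcomes, as normally run, discards subjects with any missing occasion and uses no Day 0 covariate; a mixed model is a cheap improvement to Aim 3

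*Combined protocol and SAP*

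**What the plan says.** Specific Aim 3 (section 1.0) is to "Compare healed wound characteristics, Patient Reported Outcomes and Health-related Quality of Life Outcomes between treatment groups". The Analytic Plan in section 3.1 gives the method: "Repeated Measure Analysis of Variance (ANOVAs) will be performed to assess differences in PROs with the days since wounding as the Within-Subjects factor", with treatment group as the between-subjects factor. It adds that "Bonferroni post-hoc analyses may be performed for all statistically significant main effects". On software it says "Analysis will be performed using SPSS", without naming a procedure. No covariate, missing-data rule or main contrast for these outcomes appears in the text available to this review.

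On timing, the section on Follow-up Visits (Visits 2-8) lists "subject report questionnaires consisting of SF-12, Wound Experience and Satisfaction questionnaires, Vancouver Scar Scale, POSAS Questionnaires". The Day 0 visit has "Completion of Subject Self-report questionnaires that pertain to the burn wound, pain, and other symptoms that experience", but names no instruments. That makes up to eight occasions. For detail the Procedural Summary points elsewhere: "Reference to the Schedule of Events included with Protocol for additional detail of study procedures". That schedule is not in the available text, so which instrument is scored when, and on which day each visit falls, is not known here.

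The Sample Size Estimation allows for 10% attrition (100 enrolled to retain 90). It states no power for patient-reported outcomes.

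**The concern.** Two features of the named method matter.

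- **Incomplete subjects.** The usual repeated-measures ANOVA procedure in SPSS needs a score at every level of the time factor. A subject who attends five follow-up visits and then leaves contributes nothing. The analysed set is then defined by what happens after randomization, and scores already collected go unused.
- **The Day 0 score.** If an instrument such as SF-12 is scored before treatment, the plan makes no use of that score as a covariate. Entered as a level of time, it is averaged into the group main effect, and a constant post-baseline effect shrinks to 7/8. Left out, its prognostic information is lost.

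Aim 3 would then rest on less information than the trial collects.

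**Working it through.** **The plan's figure.** 90/(1 - 0.10) = 100, so the attrition allowance reproduces. There is no stated figure for patient-reported outcomes to reproduce.

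**Inputs from the protocol.** Seven follow-up visits (Visits 2-8), a possible Day 0 score, and 10% attrition.

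**Assumptions, none of them in the documents.** Unit variance; within-subject correlation r = 0.3, 0.5 or 0.7; compound symmetry (CS) or first-order autoregressive (AR1) structure; the timing of departures; per-visit miss rates; a treatment effect constant after baseline. Efficiency is the mixed-model variance of the treatment difference averaged over seven follow-ups, divided by the ANOVA variance for the group effect. Factors common to both cancel.

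**Formulas**

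- ANOVA on follow-ups: w'Vw / c, with w = 1/7 at each visit and c the fraction with complete data. Under CS, w'Vw = r + (1 - r)/7.
- ANOVA with Day 0 as a level: u'Su / [(7/8)² c], with u = 1/8 at each of eight occasions. Under CS, u'Su = r + (1 - r)/8.
- Mixed model: w'(Σ p V⁻¹)⁻¹w, summed over missing-data patterns with probability p. V is taken conditional on Day 0 where that score is a covariate. With no missing data under CS this is r - r² + (1 - r)/7.

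**1. Attrition alone, no Day 0 score.** Take CS and r = 0.5. The ANOVA variance is 0.5714/0.90 = 0.6349. If the last follow-up attended by leavers is uniform over 0-6, the mixed-model variance is 0.5882, and 0.5882/0.6349 = 0.926. If leavers attend no follow-up, both methods use the same 90% and efficiency is 1.00. If all leave after Visit 7 (six follow-ups attended), it is about 0.90. The protocol's 10% therefore fixes a range of 90-100%. Under the uniform pattern, about 10 leavers × 3 visits = 30 collected scores per instrument are discarded per 100 subjects.

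**2. Intermittent misses, no Day 0 score.** The complete fraction is 0.98⁷ = 0.868 at 2% missed per visit and 0.95⁷ = 0.698 at 5%.

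**3. Day 0 score available, no missing data.** Take CS and r = 0.5. The baseline-adjusted mixed model has 0.25 + 0.0714 = 0.3214. Day 0 as a level: 0.5625/0.7656 = 0.7347, so 0.3214/0.7347 = 0.437. Day 0 left out: 0.3214/0.5714 = 0.562.

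| Scenario | CS, r = 0.3/0.5/0.7 | AR1, r = 0.3/0.5/0.7 |
|---|---|---|
| 10% attrition, uniform departure | 0.934/0.926/0.920 | 0.950/0.945/0.936 |
| 2% missed per visit | 0.873/0.871/0.869 | 0.877/0.873/0.870 |
| 5% missed per visit | 0.709/0.704/0.701 | 0.717/0.708/0.702 |
| Day 0 as a level | 0.612/0.437/0.262 | 0.850/0.802/0.678 |
| Day 0 left out | 0.775/0.562/0.340 | 0.984/0.942/0.819 |

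The last two rows concern the group main effect. The group-by-time test is not diluted by entering Day 0 as a level.

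**The case against.** The plan does not state that incomplete subjects are dropped. That follows from the usual procedure for the named method and the absence of another rule in the available text. Some protocol pages and the Schedule of Events were not available, so a rule may exist there. This stands as a limit; one sentence from the sponsor would settle it.

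The large losses rest on inputs not in evidence. No instrument is shown to be scored at Day 0 or at all eight occasions, and the miss rates are assumed. Compound symmetry makes a score taken just after the burn as predictive of Visit 8 as of Visit 2. If follow-ups correlate 0.5 with each other but Day 0 only 0.1 with each, efficiency is 90% with Day 0 as a level and 98% with it left out. The group main effect is also only one reading of the treatment test: the design yields a group-by-time test too, and the sentence on post-hoc comparisons is permissive. Faster healing might produce curves that converge, not a constant difference. All of this stands, so those figures are conditional.

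A reader might also infer that complete cases for the Wound Experience Questionnaire would be the slow healers, because "The questionnaire is used for wounds early into the healing process and wounds that have dressings". The documents do not support that as a finding. The questionnaire is listed for Visits 2-8 with no healing condition; the proviso about unhealed wounds is attached to dressing and treatment application. If scores did stop at healing, a mixed model would not settle what is being estimated afterwards.

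**Conclusion.** The point holds as a modest improvement to Aim 3. The named method, as normally run, drops partial follow-up and makes no use of a Day 0 score as covariate, and a better method is available in the same software.

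On the protocol's own attrition, the ANOVA has 90-100% of the mixed model's efficiency, so the loss may be nil. Losses to about 70-72% need an assumed 5% missed per visit. The ranges 26-85% (Day 0 as a level) and 34-98% (Day 0 left out) need a Day 0 score, r of 0.3-0.7, a constant effect and the group main effect as the test.

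Two stronger conclusions might be drawn and are not supported: that Aim 3 will be biased, and that a large loss of information is built into the plan. Selection after randomization makes bias possible; nothing in the documents shows it.

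**What to change.** Replace the ANOVA with a linear mixed model (MIXED in SPSS) on all available follow-up scores of randomized subjects:

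- **Terms:** treatment, scheduled visit and treatment-by-visit, with the Day 0 score as covariate for each instrument collected at Day 0.
- **Covariance:** unstructured within subject (7 × 8/2 = 28 parameters), with a prespecified simpler fallback if it does not converge, for example heterogeneous Toeplitz and then heterogeneous first-order autoregressive. State the degrees-of-freedom method.
- **Main contrast for SF-12 (PCS and MCS):** the treatment difference averaged over follow-up visits. Report treatment-by-visit estimates beside it.
- **Scar scales and Wound Experience Questionnaire:** the sponsor should choose and prespecify the visit from the Schedule of Events, and say whether the questionnaire is scored after healing. No power gain is claimed for these instruments.

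The cost is analysis-plan wording, slightly more modelling work and an explicit missing-at-random assumption. Subjects with no follow-up score, or with no Day 0 score where it is a covariate, still do not contribute. No new data, patients or software are needed.

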NCT number: NCT04601532

Official Title: Randomized Controlled Trial Assessing a Novel Glycopolymer Compound in the Treatment of Superficial Partial-Thickness Burns

Study Protocol Document Date: 8/17/2020

TITLE: Randomized controlled trial assessing a novel glycopolymer compound in the treatment of superficial partial-thickness burns.

Abstract: Current effective dressings for burn wounds contain silver (nanoparticulate or ionic), hypochlorite, hydrogen peroxide, sulfa agents, chlorhexidine, iodine or other dilute antiseptics meant to provide some measure of antimicrobial protection. However, all of these materials have some proven limitations in facilitating wound healing and also have notable local and systemic adverse effects. None of the current clinical treatments enhance healing and/or reduce scar formation. The purpose of this study is to test the safety and effectiveness of SynePure™ Wound Cleanser when used in combination with Catasyn™ Advanced Technology Hydrogel for the treatment of superficial partial-thickness burn wounds.

This study is an investigator initiated, single site, University of Pittsburgh, prospective, parallel group, randomized controlled trial comparing SynePure Wound Cleanser and Catasyn Advanced Technology Hydrogel (intervention group) to the current gold standard treatment Silvadene (control group). Both groups will receive the same care other than the treating agent. Subjects will be recruited from the UPMC Mercy Burn Center adult patient pool who have sustained superficial partial-thickness burn wounds that comprise ≤10% of total body surface area (TBSA).

1.0 Objective and Specific Aims:

Primary Objective: To test the effectiveness of SynePure Wound Cleanser when used in combination with Catasyn Advanced Technology Hydrogel for the treatment of superficial partial-thickness burn wounds as compared to standard of care treatment.

Secondary Objective: To test the ongoing safety of SynePure Wound Cleanser when used in combination with Catasyn Advanced Technology Hydrogel for the treatment of superficial partial-thickness burn wounds as compared to standard of care treatment.

Hypothesis: SynePure Wound Cleanser when used in combination with Catasyn Advanced Technology Hydrogel is safe in humans and improves time to heal and infection rates in superficial partial-thickness burn wounds when compared to standard of care treatment.

Specific Aims:

- 1) Compare re-epithelialization rates between treatment groups.

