4. Progression; recategorization of the wound to a more advanced state deep partial thickness, full thickness. Failure to heal with 21 days of injury also may be determined as progression by the investigator.

4.0 Human Subjects:

4.1 General Characteristics:

Inclusion criteria:

- 18 years of age or older, Male and Female
- Ability to provide informed consent
- Patients who have sustained superficial, partial thickness burn wounds ≤ to10% of total body surface area (TBSA)
- Patients otherwise in good general physical and mental health, as per the investigator's clinical judgment

Exclusion criteria:

- Inability to provide informed consent
- Deep partial-thickness burns and full-thickness burns
- Radiation, chemical or electrical burn injury
- Patients with burns primarily located to the face, genitals, or span across joints
- Patients whose burn injury was ≥ to 48 hours prior to entry into the UPMC Mercy Burn Clinic.
- Patients with uncontrolled cerebrovascular disease, cardiovascular disease, concurrent endocrine, hepatic or renal disease, or other severe conditions for whom, in the investigators' discretion would render study participation unsafe
- Current pregnancy
- Patients with concurrent burn related injuries or inhalation injury that would put the patient at increased risk, per physician discretion
- Any condition to which in the investigator's discretion would render study enrollment a safety concern for the patient.

All patients who present to the UPMC Mercy ER or Burn Center, whose burns are assessed to be superficial, partial thickness burns, and who also meet the study's eligibility criteria in the opinion of the referring physician will be considered for participation.

The racial, gender and ethnic characteristics of the proposed subject population reflects the demographics of Pittsburgh and the surrounding area and/or the patient population of the University of Pittsburgh Medical Center. We shall attempt to recruit subjects in respective proportion to these demographics. No exclusion criteria shall be based on race, ethnicity, gender, or HIV status.

The study will plan to enroll 115 subjects in order to randomize 100 subjects, to either the intervention group (SynePure Wound Cleanser and Catasyn Advanced Technology Hydrogel) or the control group (Silvadene). It is expected that some subjects will not meet screening criteria after they are consented, and will therefore not proceed forward to randomization.

4.4 Recruitment Procedures:

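### The progression definition lets a wound unhealed at 21 days count as progression at the investigator's discretion, so late healing is mixed into an outcome that Aim 2 defines by depth

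*Combined protocol and SAP*

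**What the plan says.** Section 1.0, Aim 2, states the comparison in terms of depth: "Compare rates of infection, complication and progression of the wound to deep partial/full thickness between treatment groups".

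Section 3.1, Outcome definitions, item 4, begins in the same terms: progression is recategorisation to deep partial or full thickness. It then continues: "Failure to heal with 21 days of injury also may be determined as progression by the investigator". No criterion is given for when the investigator should do so. Item 1 of the same list defines a healed wound only by 90% reepithelialisation, with no reference to depth.

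Section 3.1, Analytic Plan, treats progression as one rate per group: "Infection, complication, and progression rates will be compared using the Chi-squared test or the Fisher exact test". The available text does not ask for the two routes to be reported separately.

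Two further places bear on the size of the problem. The hypothesis in section 1.0 is that the intervention "improves time to heal and infection rates in superficial partial-thickness burn wounds when compared to standard of care treatment". The Sample Size Estimation gives the expected healing times: "Given an assumed median time of 15 days to healing for the Silvadene comparator group", with "the minimal median difference of three (3) days to healing is determined to be the clinically relevant difference".

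**The concern.** Aim 2 asks whether wounds became deeper. Item 4 also admits wounds that are merely slow to heal. The word also makes this an additional route, and the word may makes it optional; nothing ties it to a depth finding. To the extent that it is used for wounds not judged deeper, the progression rate is a mixture of depth conversion and late healing, in proportions that nobody can recover from the planned report.

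This matters because late healing is what the trial expects to differ. If the intervention speeds healing, fewer of its wounds are unhealed at 21 days. Even when every unhealed wound is treated alike in both groups, and depth conversion is identical, the healing effect carries over into the progression rate. A reader who sees faster healing and less progression could take one effect for two, and credit the product with preventing depth conversion that it did not prevent.

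**Working it through.** **Inputs from the plan.**
- Control median 15 days; intervention median 15 − 3 = 12 days (section 3.1, Sample Size Estimation).
- Effect: "a corresponding hazard ratio of 0.8 for the intervention group is anticipated" (same place).
- Roughly constant hazard over the period of study (section 3.1, Analytic Plan).
- 45 wounds per group (Sample Size Estimation), used here only as a denominator; its adequacy for time to healing is a separate matter.

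**Inputs assumed, because the documents give none.** True depth conversion c = 5% in each group, and labelled share l = 50% of eligible unhealed wounds in each group. Ranges are shown in step 3.

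**Step 1: the plan's own figure.** Under constant hazard the rate is ln 2 / median, so the control-to-intervention ratio is (ln 2/15)/(ln 2/12) = 12/15 = 0.8. This reproduces the stated ratio and confirms that the plan is working with constant hazard (the intervention's healing hazard relative to control is 1/0.8 = 1.25). The plan states no progression rate, so there is none to reproduce.

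**Step 2: wounds eligible for the discretionary label.** Unhealed at 21 days: u = 0.5^(21/median).
- Control: 0.5^(21/15) = 0.379, or 17.1 of 45.
- Intervention: 0.5^(21/12) = 0.297, or 13.4 of 45.

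The clause counts from injury, and the exclusion criteria in section 4.1 require injury less than 48 hours before clinic entry. If the medians run from Day 0 and Day 0 is the day of entry, 21 days from injury is study day 19 to 21. At day 19 the figures are 0.416 and 0.334.

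**Step 3: share of counted events that are not depth changes.** Two extremes for how converted and unhealed wounds overlap:
- Independent: p = c + (1 − c)·u·l. Control 0.05 + 0.95 × 0.379 × 0.5 = 0.230; intervention 0.05 + 0.95 × 0.297 × 0.5 = 0.191.
- Every converted wound is also unhealed: p = c + (u − c)·l. Control 0.05 + 0.329 × 0.5 = 0.214; intervention 0.05 + 0.247 × 0.5 = 0.174.

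The share without depth change is 1 − c/p: 78.3% and 73.9% (independent), 76.7% and 71.2% (full overlap).

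Varying c from 2% to 10% and l from 25% to 100% at constant hazard gives these extremes:
- Lowest (intervention, full overlap, c = 10%, l = 25%): p = 0.10 + 0.197 × 0.25 = 0.149, share 33%.
- Highest (control, independent, c = 2%, l = 100%): p = 0.02 + 0.98 × 0.379 = 0.391, share 95%.

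**Step 4: chance of a significant progression test when depth conversion is equal.** Exact enumeration of all 46 × 46 outcomes, 45 per group, significance at p ≤ 0.05, chi-squared without continuity correction and two-sided Fisher.

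| Event rates, control v intervention | Chi-squared | Fisher |
|---|---|---|
| 0.230 v 0.191 (l = 50%, independent) | 7.9% | 4.1% |
| 0.214 v 0.174 (l = 50%, full overlap) | 8.3% | 4.3% |
| Equal groups, about 0.20–0.23 | about 5.4% | about 2.6% |
| Equal groups, 0.05 (depth changes only) | 4.9% | 0.6% |
| 0.410 v 0.332 (l = 100%, independent) | 12.0% | 8.3% |
| 0.379 v 0.297 (l = 100%, full overlap) | 13.5% | 9.2% |

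The fair reference for the first two rows is the third, which has a similar event rate and no difference. The 0.6% in the fourth row mainly reflects how conservative Fisher's test is with about 45 × 0.05 = 2 events per group. The rise due to the healing difference is therefore 7.9 − 5.4 = 2.5 to 8.3 − 5.4 = 2.9 points for chi-squared, and 4.1 − 2.6 = 1.5 to 4.3 − 2.6 = 1.7 points for Fisher.

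**Step 5: the case of no effect.** If the clause is applied only to wounds judged deeper, p = c in each group and the mixing disappears.

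**The case against.** The strongest defence is that item 4 is prespecified. A difference in the outcome as defined, caused by fewer unhealed wounds, is a real difference in that outcome, and the Kaplan-Meier curves let a reader see the healing effect alongside it. That stands as far as it goes: this is not a false positive for item 4 as written. It does not answer Aim 2, which names depth and describes no composite.

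A second defence is that the clause means late healing should prompt a fresh judgement of depth. That is a sensible clinical reading, and under it there is no problem. But the sentence does not require a depth finding, so the reading has to be supplied by the reader. The Schedule of Events and some later parts of the protocol were not in the text available for this review and could hold assessment detail.

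A third is that the conversion and labelling rates are invented. That is correct; only the eligible fractions in step 2 rest on the plan's figures, and the share in step 3 should be read with its range.

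Three stronger readings are tempting, and the documents do not support them.
- A reader might infer that false positives rise sharply. Healing times with a rising hazard (Weibull shape 2 or 3) and the same medians give 15–18% by chi-squared. Those shapes imply healing-hazard ratios of (15/12)² = 1.56 and (15/12)³ = 1.95, against the plan's 1.25, and depart from its constant-hazard statement. Holding the ratio at 0.8 gives 8–9% (chi-squared) and 3–4% (Fisher) for all three shapes.
- A reader might infer a seven-fold rise for Fisher's test from 0.6% to about 4%. Most of that comes from the higher event count, as step 4 shows.
- A reader might infer that investigators would label the groups differently. Uneven use could matter: 17 v 7 of 45 gives Fisher p = 0.031, whereas even-handed labelling of all eligible wounds, 17 v 13, gives p = 0.50. The available text describes no masking, but nothing in it shows differential labelling, and no result in the verdict depends on it.

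**Conclusion.** The point holds as an interpretation problem for one of the three Aim 2 event rates. Aim 2 and item 4 do not describe the same outcome, and the single planned comparison cannot tell them apart. On the plan's medians and constant hazard, roughly three or four wounds in ten would be eligible for a label that needs no depth finding, with more in the control group if the hypothesis is true. With the assumed 5% conversion and 50% labelling, about three-quarters of counted events would not be depth changes.

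The effect on the significance test is small on plan inputs, about 2 to 3 points for chi-squared and 1 to 2 for Fisher, so the case should not be argued as error inflation. The harm is that one effect may be reported as two. Severity is minor to moderate. The definition of healing, the log-rank analysis and patient care are not affected.

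**What to change.** Reconcile Aim 2 with item 4. For the Aim 2 analysis, count as progression only wounds recategorised on examination to deep partial or full thickness. An unhealed wound that is judged deeper still counts by this route.

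Report the proportion unhealed at 21 days from injury as a separate outcome, by one rule for every subject. Use the Kaplan-Meier estimate at that day, so that dropouts are handled as in the healing analysis, and state whether time runs from injury or from Day 0. The data are already planned: at the follow-up visits, "These visits will consist of wound evaluation to assess for healing" (section 3.0).

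A composite that counts every unhealed wound is not recommended as the main option. It removes the discretion but increases the overlap with healing (12.0–13.5% by chi-squared and 8.3–9.2% by Fisher in step 4). Only separate reporting of the components would address the mixing.

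The cost is one sentence in the outcome definitions and one extra reported proportion. There will be fewer progression events and less power for that secondary comparison, though the events lost are those that do not answer Aim 2. Depth recategorisation remains an investigator's judgement, so some scope for assessor bias stays. The 21-day estimate will be only as precise as the visit spacing, which the available text does not give. The change affects how outcomes are counted, not how patients are treated.
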